**Clinical Study Protocol**  
**Johnson & Johnson Vision Care, Inc.**

**If the subject is randomized to ARM 1, proceed to:  
ARM 1 STUDY PROCEDURES, Visit 2, Step 2.1.**

**If the subject is randomized to ARM 2, proceed to:  
ARM 2 STUDY PROCEDURES, Visit 2, Step 2.1**

**ARM 1 STUDY PROCEDURES**

**VISIT 2 (14 ± 2 days following Visit 1)**

**Subjects must present with study lenses on eye for at least 2 hours.**

| ARM 1              |   |  |     |
|---------------------------|---|--|-----|
| Visit 2: 2-Week Follow-Up |   |  |     |
| Step                      | Procedure   | Details  |     |
| 2.1.                      | Adverse Events and Concomitant Medications Review | Review any changes to the subject's medical history or concomitant medications from the previous study visit. Record any changes, and any adverse events.                                      | N/A |
| 2.2.                      | Wear time   | Record the average wear time and comfortable wear time.  | N/A |
| 2.3.                      | Compliance  | Confirm compliance with the prescribed wear schedule.  | N/A |
| 2.4.                      | Subject Reported Ocular Symptoms                  | Subjects will respond to a verbal open-ended symptoms questionnaire.   |     |
| 2.5.                      | CLDEQ-8 Questionnaire                             | The subject will respond to the CLDEQ-8 Questionnaire (Appendix A)   |     |
| 2.6.                      | Follow-up questionnaires                          | The subject will respond to the CLUE and MRD Follow Up Questionnaire (Appendix A)  |     |
| 2.7.                      | Entrance Visual Acuity                            | Record the distance Snellen visual acuity with the contact lenses (OD, OS) to the nearest letter. Subjects must read the smallest line until at least 50% of the letters are read incorrectly. |     |

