### **2.3. Hypotheses**

Primary Hypothesis:

The Primary hypothesis will be evaluated between the two study arms; only the first period will be considered for the second study arm.

| Primary Hypotheses |   |
|--------------------|---|
| Endpoint           | Hypothesis  |
| CLUE Comfort       | The Test lens will be non-inferior to the Habitual lens with respect to the change in CLUE comfort score from baseline at 2-week follow-up. A non-inferiority margin of -5 points on the CLUE scale will be used. |

Secondary Hypotheses:

The primary hypothesis must be met in order to test the secondary hypotheses. The secondary hypothesis regarding the change in CLDEQ-8 Scores will be evaluated between the two study arms; only the first period will be considered for the second study arm. The remaining two secondary hypotheses will be evaluated within the second study arm only.

| Secondary Hypotheses          |  |
|-------------------------------|--|
| Endpoint                      | Hypothesis   |
| Change in CLDEQ-8 Total Score | The Test lens will be non-inferior to the Habitual lens with respect to the change in CLDEQ-8 total score from baseline at 2-week follow-up. A non-inferiority margin of 3 points on the CLDEQ-8 scale will be used. |
| CLDEQ-8 Total Score           | The Test lens will be non-inferior to the Habitual lens with respect to CLDEQ-8 total score at 2-week follow-up. A non-inferiority margin of 3 CLDEQ-8 points will be used.  |
| CLUE Comfort                  | The Test lens will be non-inferior to the Habitual lens with respect to CLUE comfort score at 2-week follow-up. A non-inferiority margin of -5 CLUE points will be used.   |

The primary hypothesis must be met in order to satisfy the objective of the study.

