### **5.2. Masking**

This study will be a subject-masked to the Test lens. Subjects will be unaware of the identity of the Test lens as the Test lens will be over labeled. Due to the nature of the study design, each subject will be aware of the identity of the Control lens as it is her/his habitual lens. Investigators and clinical site personnel involved in the data collection may be aware of the identity of the investigational product.

Subjects who have had their treatment assignment unmasked are expected to return for all remaining scheduled evaluations. If necessary, subjects who are discontinued may be replaced to reach the subject completion target.

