Table 9 displays the sample size estimates for the primary endpoint of CLUE Comfort score, and the secondary endpoint of CLDEQ8- Scores for different scenarios of effect sizes. CLDEQ-8 power analysis was provided for informational purposes. All Sample size calculations were performed with 80% power and 2-sided alpha=0.05. With respect to CLDEQ-8 Scores, for ARM1 a standard deviation of 7.17 was utilized (See Table 7 ), while a standard deviation of 5.0 was utilized for ARM2 in each calculation for the various effect sizes. The different effect sizes for CLDEQ-8 scores were based on the historical effect sizes provided in Table 7. Historically, on average AO1D improved CLEQ8-scores about 7 points after 2-weeks of wear. The power analysis for CLDEQ8-scores is displayed in Table 9 below. With respect to CLUE comfort scores, for ARM1 a standard deviation of 25.21 was used (See Table 8) while, a standard deviation of 18.12 was utilized for ARM2 in the calculation for each scenario. Due to the varying effect sizes displayed in Table 8 above, effect sizes of 3, 5 and 9 were utilized as a more conservative estimate for the sample size calculation since there was a high a difference observed between AO1D and subjects' habitual lenses with respect to CLUE Comfort (22.6 points) in ██████.

Sample size and power calculations for each endpoint and scenario were calculated using a 2-sided Satterthwaite t-test assuming unequal variances using the POWER^11 procedure in SAS Version 9.4.

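### At follow-up, staff who may know the lens check compliance and interview the subject about symptoms just before the self-reported endpoints, leaving an avoidable route for lens-dependent influence

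*Combined protocol and SAP*

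**What the plan says.** Section 5.2 masks subjects to the test lens by over-labelling. The control is each subject's own lens and is known to them. Of staff it says: "Investigators and clinical site personnel involved in the data collection may be aware of the identity of the investigational product".

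Section 7.2 sets out the visits as numbered steps. At ARM 1 Visit 2 these are adverse-event and medication review (2.1), wear and comfortable wear time (2.2), compliance (2.3), the symptoms step, where "Subjects will respond to a verbal open-ended symptoms questionnaire" (2.4), CLDEQ-8 (2.5) and CLUE/MRD (2.6). ARM 2 Visit 2 has the same steps under the same numbers. ARM 2 Visit 3 repeats them as 3.1 to 3.6, with Preference at 3.7.

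At Visit 1, CLDEQ-8 is step 1.6 and CLUE/MRD step 1.8, both before randomization (1.16). The verbal symptoms step is 1.23, after the study lens has been fitted.

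ARM 2 step 2.5 carries a note under which a subject who no longer scores at least 15 on CLDEQ-8 is discontinued. ARM 1 step 2.5 has no such note.

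**The concern.** The primary endpoint is change in CLUE comfort, and the three secondary endpoints are CLUE comfort and CLDEQ-8 scores. All are the subject's own ratings of comfort and dryness. Subjects know when they are wearing their habitual lens, so the masking of AO1D is the main protection for the test rating.

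A conversation about symptoms and compliance, held minutes before the rating by someone who may know which lens was worn, is a route by which that rating could be coloured. ARM 2 Visit 2 adds an asymmetry: the interview comes directly before a score that decides whether the subject continues, and ARM 1 has no equivalent. A nudge towards reporting symptoms there would worsen control scores and favour the test lens. At stake is a differential shift in the primary contrast, judged against a margin of only 5 CLUE points.

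**Working it through.** **1. What precedes the questionnaires at each visit (section 7.2)**

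| Before CLDEQ-8 and CLUE | Visit 1 | ARM 1 Visit 2 | ARM 2 Visit 2 | ARM 2 Visit 3 |
|---|---|---|---|---|
| History/medications (with AE review at follow-up) | 1.3 | 2.1 | 2.1 | 3.1 |
| Wear and comfortable wear time | 1.5 | 2.2 | 2.2 | 3.2 |
| Compliance | none | 2.3 | 2.3 | 3.3 |
| Verbal symptoms interview | none | 2.4 | 2.4 | 3.4 |
| Score decides continuation | eligibility, before randomization | no | yes (2.5) | no |

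The staff-led items present at follow-up but not at baseline are compliance, the symptoms interview and the adverse-event part of the review. The order is identical across the three follow-up visits.

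**2. Does a common order effect bias the tests?**

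Write B for the baseline mean, F for the follow-up mean free of any order effect, and c for the shift caused by questioning before the rating. The primary contrast (section 14.5) is

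(F1 + c1 - B1) - (F2 + c2 - B2) = [(F1 - B1) - (F2 - B2)] + (c1 - c2),

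with 1 = ARM 1 and 2 = ARM 2, first period. If c1 = c2, the bias is zero. The first secondary contrast has the same form. The other two secondaries (section 14.6) compare Visit 2 with Visit 3 within ARM 2, with baseline only as a covariate, so a common c cancels there too. It stays in each arm's raw change from baseline. Only c1 - c2, a shift that differs by lens, can affect a test.

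**3. Reproducing the plan's figure to obtain the standard error**

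Inputs from section 14.2: "All Sample size calculations were performed with 80% power and 2-sided alpha=0.05"; the figures were "calculated using a 2-sided Satterthwaite t-test assuming unequal variances"; SDs of 25.21 (ARM 1) and 18.12 (ARM 2). From section 2.3: "A non-inferiority margin of -5 points on the CLUE scale will be used". The distance to the margin is the effect plus 5. A Satterthwaite t-test using the noncentral t gives:

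| Effect | Distance | n per arm computed | Table 9 | Power |
|---|---|---|---|---|
| 3 | 8 | 120 | 120 | 80.2% |
| 5 | 10 | 77 | 77 | 80.1% |
| 9 | 14 | 40 | 40 | 80.3% |

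Table 9 is reproduced. At 40 per arm:

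SE = sqrt((25.21² + 18.12²)/40) = sqrt((635.54 + 328.33)/40) = sqrt(24.10) = 4.91 CLUE points, on 70.8 degrees of freedom.

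**4. What a differential shift would do**

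The documents give no value for c1 - c2, so the range is an assumption. With a shift of b points favouring the test lens and a true difference of -5, type I error is P(T > t), where T is noncentral t with noncentrality b/4.91 and t is the upper 2.5% point. With a shift of b against the test lens and a true effect of 9, power uses noncentrality (14 - b)/4.91.

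| b (assumed) | Type I error, favouring test | Power, against test |
|---|---|---|
| 0 | 0.025 | 80.3% |
| 1 | 0.039 | 74.3% |
| 2 | 0.060 | 67.4% |
| 3 | 0.087 | 59.9% |
| 5 | 0.170 | 44.0% |

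**The case against.** The strongest reply is that the shared order disarms most of the worry. A reader might infer that the change score in the primary test mixes two measurement conditions and is biased by that. The documents do not support this: step 2 shows that a common effect drops out of every primary and secondary contrast, and none of those hypotheses tests within-arm change. This part of the reply stands in full.

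A reader might also infer that the visit order is wholly reversed between baseline and follow-up. It is not. History, habitual-lens details and comfortable wear time (1.3 to 1.5) precede the questionnaires at Visit 1 as well. Step 1.23 is not the counterpart of 2.4 either: it follows fitting of the study lens, and ARM 2 Visit 2 has its own post-fit interview at 2.17.

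Three further points have some force. Section 5.2 says staff may be aware of the lens, not that they are. Influence could also arise during fitting and dispensing, which reordering would not touch. And the questionnaires in Appendix A and the patient-reported-outcomes work instruction in Appendix D cannot be read, so a rule on order or self-completion may exist there. Nor does the protocol state outright that step numbers bind the order, although section 7.2 uses them that way, for example in the instruction to repeat steps 1.18 to 1.21.

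These points limit how much the change can achieve. They do not justify placing the symptoms interview immediately before the primary rating, since nothing in compliance or the interview is needed to complete the questionnaires.

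**Conclusion.** The point holds as a small, avoidable weakness in procedure, not as a demonstrated bias. The residual risk is an influence that differs by lens. It rests on three features of the text: staff may know the lens, the control is open label, and only ARM 2 Visit 2 ties continuation to the CLDEQ-8 score that follows the interview.

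Its size cannot be derived from the documents. The illustration (type I error of about 0.039 for a 1-point shift) assumes the shift, and also takes the plan's SDs and 40 completers per arm as given. The 18.12 used for ARM 2 is Table 8's SD of habitual baseline scores, not of a change, so the true standard error may differ.

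Two stronger conclusions should be resisted. About 120 follow-up assessments (40 + 40 + 40) come after the interview, but that counts scores sharing an order, not biased scores; the primary contrast uses 80 of them. And nothing in the documents shows that staff do influence ratings in either arm.

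**What to change.** In section 7.2, at ARM 1 Visit 2 and ARM 2 Visits 2 and 3, place CLDEQ-8, CLUE/MRD and (Visit 3) Preference ahead of the compliance and verbal symptoms steps (2.3 to 2.4, 3.3 to 3.4). State that the subject completes them without staff input.

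Leave the history/adverse-event review and wear-time steps ahead of the questionnaires, matching Visit 1 steps 1.3 to 1.5. Moving those as well would create a new difference from baseline. The adverse-event review would then still precede the ratings, a residual accepted for the sake of that match.

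Two consistency items go with the change. If the redacted work instruction already sets an order, align section 7.2 with it. And because the note at ARM 2 step 2.5 sends some subjects straight to the final evaluation, say whether the moved steps are still recorded for them, reading it with section 8.2, under which the current visit is completed for discontinued subjects.

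The cost is renumbering, with the compliance check and interview a few minutes later in the visit. Sample size, procedures and analysis are unchanged.

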**Clinical Study Protocol**  
**Johnson & Johnson Vision Care, Inc.**

| ARM 1              |                                |   |     |
|---------------------------|--------------------------------|---|-----|
| Visit 2: 2-Week Follow-Up |                                |   |     |
| Step                      | Procedure                      | Details   |     |
| 2.8.                      | Subjective Lens Fit Assessment | 
Evaluate overall lens fit acceptance (acceptable or unacceptable) based on centration, movement and other fitting characteristics.
 
An unacceptable fit is deemed by one of the following criteria:
 
 
• limbal exposure at primary gaze or with extreme eye movement.
 
• edge lift.
 
• excessive movement in primary and up gaze.
 
• insufficient movement in all three of the following conditions: primary gaze, up gaze, and Josephson push up.
 
 
NOTE: if lens fit is unacceptable subject will be discontinued from the study.
 |     |
| 2.9.                      | Lens Removal and Discard       | 
The lenses will be removed by the subject and discarded.
 
Proceed to Final Evaluation (Step F.1)
  | N/A |

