# **Clinical Study Protocol**

## **Johnson & Johnson Vision Care, Inc.**

### **Safety Endpoints:**

Adverse events, lens fitting characteristics, slit lamp findings, entrance/exit visual acuity, subject reported ocular symptoms

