**FINAL EVALUATION (ARM 1 & ARM 2)**

The final evaluation will ordinarily take place immediately following the last scheduled follow-up visit per the study protocol. It may also take place at any point the subject discontinues the study or is terminated from the study.

| Final Evaluation |                              |   |                          |
|------------------|------------------------------|---|--------------------------|
| Step             | Procedure                    | Details   | [REDACTED]               |
| F.1              | Final Exam Form              | Indicate if the subject completed the study successfully. If subject discontinued from the study, indicate the reason.  |                          |
| F.2              | Exit Refraction              | Perform bare-eye subjective spherocylindrical refraction with a phoropter and record the best-corrected distance visual acuity (OD and OS) to the nearest letter.

Note: This step is not necessary if the subject was exited due to screen failure.   | [REDACTED]
[REDACTED] |
| F.3              | Exit Slit Lamp Biomicroscopy | FDA Slit Lamp Classification Scale will be used to grade the findings.

If the clearance of the fluorescein needs to be expedited, preservative-free rewetting drops or saline may be instilled. This step is not necessary if the subject was exited due to screen failure.

Note: This step is not necessary if the subject was exited due to screen failure, or if biomicroscopy was performed as part of the final follow-up visit procedures (i.e., immediately prior to the final evaluation). | [REDACTED]               |

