### **8. SUBJECTS COMPLETION/WITHDRAWAL**

#### **8.1. Completion Criteria**

Subjects are considered to have completed the study if they:

- provide informed consent,
- are eligible to participate the study, and
- completed all study visits.

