#### **Per-Protocol Population:**

All subjects who successfully complete all visits and do not substantially deviate from the protocol as determined by the trial cohort review committee prior to database hard lock. Justification for the exclusion of subjects with protocol deviations from the per-protocol population set will be documented in a memo to file.

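### An unacceptable fit grade at a two-week visit, given after comfort and dryness are recorded, can cost a subject with complete endpoint data a place in the Per-Protocol set

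*Combined protocol and SAP*

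**What the plan says.** - **Order of steps.** At ARM 1 Visit 2, CLDEQ-8 is answered at Step 2.5, CLUE at Step 2.6, and fit is graded at Step 2.8. ARM 2 Visit 2 has the same order for the habitual lens. ARM 2 Visit 3 has it for AO1D (Steps 3.5, 3.6, 3.9).
- **Consequence of the grade.** All three fit steps carry the same instruction: "NOTE: if lens fit is unacceptable subject will be discontinued from the study". At ARM 1 Visit 2 and ARM 2 Visit 3, the next step removes the lenses and sends every subject to the Final Evaluation.
- **Disposition.** Final Evaluation Step F.1 reads "Indicate if the subject completed the study successfully. If subject discontinued from the study, indicate the reason".
- **Completion.** Section 8.1 asks for consent, eligibility and that the subject "completed all study visits". It sets no condition on fit.
- **Withdrawal.** The one reason in Section 8.2 that names fit concerns subjects who could not be successfully dispensed. Section 8.2 also has a discontinued subject finish the visit in progress.
- **PP set.** Section 14.3 takes "All subjects who successfully complete all visits and do not substantially deviate from the protocol as determined by the trial cohort review committee". Sections 14.5 and 14.6 assess non-inferiority on this set. For the primary and first secondary endpoints ITT is the sensitivity analysis.
- **Status of fit.** Section 2.2 lists it as a safety outcome: "Adverse events, lens fitting characteristics, slit lamp findings". Table 6 does not give it as an example of a deviation.

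**The concern.** At the two last-visit steps the note changes neither exposure nor data, because the questionnaires are done and the lenses are about to come off. It changes only how the subject is recorded. One subject can be a completer under Section 8.1 and discontinued under Step 2.8 or 3.9, and Section 14.3 does not say which status governs PP membership.

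At ARM 2 Visit 2 the note has a further effect. The subject leaves before Visit 3 and so fails the all-visits condition of the PP definition, although the habitual-lens data for the primary comparison are complete.

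Fit at two weeks is a result of the assigned lens. It is graded subjectively, after the endpoint has been given, by staff who under Section 5.2 may know which lens it is. Selecting the deciding analysis set on such a grade opens the primary comparison to post-randomization selection. An ARM 2 subject who fails AO1D fit at Step 3.9 could also take valid habitual-lens data out of that comparison, since PP membership is defined by subject and not by period.

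**Working it through.** **1. The plan's own figure.** Inputs from Section 14.2 and Table 9: SD 25.21 (ARM 1) and 18.12 (ARM 2), effect 9, margin -5, two-sided alpha 0.05, 80% power, Satterthwaite t-test.

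- Distance to the margin: 9 + 5 = 14.
- SE at 40 per arm: sqrt((25.21² + 18.12²)/40) = sqrt(963.88/40) = 4.91.
- Noncentrality: 14/4.91 = 2.85, with about 70.8 degrees of freedom. Power is 80.3%.
- The smallest adequate sample is 40 per arm, as stated. Effects 3 and 5 give 120 and 77, also as stated.

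**2. What the text decides at each step.**

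| Step | Lens graded | CLUE and CLDEQ-8 for that lens done? | Completer under 8.1? | In PP? |
|---|---|---|---|---|
| ARM 1, 2.8 | AO1D | Yes | Yes | Unclear: all visits attended, but recorded as discontinued |
| ARM 2, 2.8 | Habitual | Yes | No, Visit 3 is missed | No, on the plain wording |
| ARM 2, 3.9 | AO1D | Yes | Yes | Unclear, as for ARM 1 |

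The firmest exclusion in the text is therefore on the control side. For the other two, exclusion is suggested by the success wording in Section 14.3 and by F.1. Table 10 points the same way, because completed and discontinued subjects sum to those dispensed in the historical studies (199 + 23 = 222). Section 8.1 points the other way.

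**3. Possible size, under assumptions.** The documents give neither a rate of late unacceptable fit nor the comfort difference that goes with it. Suppose k1 of 40 ARM 1 subjects are removed, with mean CLUE change g1 points below the rest, and likewise k2 and g2 in ARM 2. Then

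shift in the PP difference (toward AO1D if positive) = (k1/40) × g1 - (k2/40) × g2.

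For ARM 1 removals only (k2 = 0), SDs unchanged, 40 - k1 subjects analysed in ARM 1 and a true all-subject difference of -5:

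| k1 | g1 | Shift (points) | One-sided type I error |
|---|---|---|---|
| 0 | – | 0 | 0.025 |
| 1 | 10 | 0.25 | 0.028 |
| 1 | 25 | 0.625 | 0.033 |
| 2 | 10 | 0.50 | 0.031 |
| 2 | 25 | 1.25 | 0.043 |
| 4 | 10 | 1.00 | 0.039 |
| 4 | 25 | 2.50 | 0.070 |

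The shift is 5% (0.25/5) to 50% (2.5/5) of the margin.

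**4. Other cases.** With two removals per arm and a 20-point gap in each, the shift is 1.0 - 1.0 = 0. With one removal in ARM 1 (gap 10) and four in ARM 2 (gap 20), it is 0.25 - 2.0 = -1.75 points, against AO1D. If removed ARM 1 subjects do not differ (g1 = 0), there is no bias and power falls from 80.3% to 79.6% (k1 = 1) or 77.4% (k1 = 4).

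**The case against.** The strongest reply is that nothing in the documents says a last-visit fit failure leaves the PP set. The cohort review committee decides before lock, Section 8.1 makes the subject a completer, and Table 6 does not list fit as a deviation. Fit also had to be acceptable at dispensing (Steps 1.20 and 1.25), so late failures may be rare. The upper illustration needs 4 of 40 subjects (10%) failing late and a 25-point gap, which exceeds the CLUE population SD of 20 in Section 2.2. ITT keeps every such subject and is the planned sensitivity analysis, and superiority is tested on ITT anyway.

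All of this stands and limits the point. It also rules out three stronger readings that a reader might infer:

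- **That the note does remove poor-fitting AO1D wearers from PP.** The text leaves this open.
- **That the bias favours non-inferiority.** The habitual lens carries the same note at ARM 2 Step 2.8, where exclusion is textually firmer. ARM 1 is graded on a newly fitted lens and the controls on a familiar one, so unequal failure rates are plausible, but no rates are given.
- **That a last-visit fit failure triggers replacement.** Section 8.2 speaks of premature discontinuation. Section 4.3 covers discontinuation before the final evaluation and leaves replacement to the sponsor's discretion. A subject with full data at the last visit is not clearly either.

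The reply does not remove the contradiction. Leaving the matter to the committee means that the deciding set may turn on an unsettled label, judged when the comfort scores already exist. ITT would show the effect of such a decision but does not decide non-inferiority.

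**Conclusion.** The point holds as a conflict between passages, with a possible but unquantified selection effect on the primary test. At ARM 1 Step 2.8 and ARM 2 Step 3.9, a subject with complete endpoint data is both a completer and discontinued. At ARM 2 Step 2.8, a control with complete primary data falls outside PP because Visit 3 is missed. Either route can change who counts in the non-inferiority comparison because of how the worn lens fitted.

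The range of 0.25 to 2.5 points toward AO1D rests on three assumptions without a source in the documents: 1 to 4 of 40 removed, a comfort gap of 10 to 25 points, and removals in ARM 1 only. Equal removals with equal gaps cancel, and heavier removal in ARM 2 reverses the sign. The matter should be settled before database lock. It is not evidence that the planned result is biased.

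**What to change.** Reconcile Step 2.8 (both arms) and Step 3.9 with F.1 and Sections 8.1, 8.2 and 14.3, so that a subject has one status.

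In Section 14.3, and in the stand-alone SAP that Section 14.1 announces, state before database lock and identically for both arms:

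- An unacceptable follow-up fit grade alone does not exclude a subject from the PP set for any comparison whose questionnaires were already completed.
- For the primary and first secondary comparisons, this means the Visit 2 data of both arms. It includes ARM 2 subjects who leave at Visit 2 because of the habitual-lens fit grade, and those who fail AO1D fit later.
- For the within-ARM 2 comparisons, a subject graded unacceptable at Step 3.9 stays in, since both lenses have been rated. A subject who left at Visit 2 has no AO1D scores to contribute.

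Report the number of such subjects by arm and step.

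The rule must cover all three steps. Covering only the AO1D steps would keep poor-fitting test wearers while still losing poor-fitting controls at the same time point. Whether wear continues or the subject is stopped for poor fit is left to the sponsor.

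The cost is a short paragraph in Section 14.3, aligned wording in the passages named, and one line in the disposition table. PP membership becomes specific to each comparison. No visit, procedure or sample-size figure changes.
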